Summaries of all baseline characteristics will be presented using means and standard deviations, medians and interquartile ranges, or frequencies and percentages, as appropriate. The groups will be compared using chi-square tests for equality of proportions for binary data (e.g. proportion of cases of influenza detected) and using independent-samples t-tests or non-parametric equivalent as appropriate for continuous data (e.g. duration of isolation facility use, etc.).

The primary outcome measure (median duration of isolation facility use) will be compared between the groups using the Mann-Whitney U test. Multivariate analysis will be performed to adjust for confounding variable in view of the non-randomised nature of the study.

12. Safety

Serious Adverse Events

The risks of respiratory tract sampling and additional blood tests being taken are minimal and where occurring are likely to be mild. No additional adverse events related to mPOCT for respiratory viruses including COVID-19 are anticipated. However active monitoring and reporting of severe adverse events will be undertaken. A Serious Adverse Event (SAE) is any adverse event that:

- Results in death

- Is life-threatening

- Requires hospitalisation or prolongation of existing hospitalisation

- Results in persistent or significant disability or incapacity
- Consists of a congenital anomaly or birth defect

In the event of a SAE, a study doctor will consider the likelihood of the event being related to the study based on the documented evidence from the treating clinicians. SAEs will be reported via the sponsor's standard forms and processes. SAEs will be reported within 24 hours of the study team learning of the SAE. In the event of a SAE, the PI will be involved in deciding whether this was a study-related event. In the event of a study-related SAE, the REC will be informed as per HRA regulations.

Participants already admitted to AMU, or another hospital ward including high dependency or an intensive care unit, or are in ED but with a decision already made to admit, are considered already hospitalised. However, an adverse event leading to prolongation of their existing hospitalisation will be counted as an SAE.

Only SAEs occurring within 30 days of enrolment or hospital discharge, whichever comes soonest, will be reported to the sponsor, with the exception of any congenital anomaly or birth defect. Congenital anomalies or birth defects will be actively recorded up to 30 days post enrolment but if discovered after this period will still be reported to the sponsor. The trial procedures are very brief and very low risk, and pregnancy commencing during the trial procedures or follow up period is both unlikely to occur and is not expected to be reported to the sponsor or REC. Participants in high dependency or intensive care units are at high risk of expected death, and therefore participants recruited in these locations who die will not be reported as an SAE to the sponsor, unless it is deemed related to the study by the PI.

The SAE conditions noted were prompted by previous respiratory virus molecular POCT studies including one that showed around 60 SAEs for just over 300 patients. A large proportion of the patient group had conditions making readmission likely and had a high background likelihood of mortality. Not a single SAE was in any way related to the study, but significant resources were taken up in reporting of the SAE without any benefit or impact upon safety. Similar criteria have been used in two previous POCT studies. Therefore, the caveats to SAE reporting for this trial have been developed to streamline the reporting process, promote efficiency and maximise safety.

Urgent safety measures

A sponsor or investigator may take appropriate urgent safety measures in order to protect research participants against any immediate hazard to their health or safety, without prior authorisation from a regulatory body. The REC must be notified immediately and in any event within three days, in the form of a substantial amendment, that such measures have been taken and the reasons why.

Protocol non-compliance and deviations

Events of protocol non-compliance or deviation will be considered by the Chief Investigator on a caseby-case basis. Where deemed necessary by the CI, advice from trials mangers, facilitators, or governance staff within UHS R&D, and as the sponsor, will be sought.

Serious breaches of GCP or protocol

Serious breaches of GCP or the protocol should be reported, by the investigators and the sponsor, within seven days to the Medicines and Healthcare products Regulatory Agency and relevant ethics committee in accordance with current regulations. A "serious breach" is a breach which is likely to effect to a significant degree the safety or physical or mental integrity of the subjects of the trial, or the scientific value of the trial.

Update to SAE reporting with Protocol Version 1.2

As of 3rd June 2020, 131 SAEs of deaths, life-threatening events, and readmissions have been reported to the sponsor with more expected to be found and therefore need reporting. All SAEs have been unrelated to the study procedures. Given the high rate of poor clinical outcomes during the COVID-19 outbreak unrelated to the study, and the high and unnecessary administrative burden without any safety benefit, SAE reporting for this trial urgently needs to be updated. Therefore, as of the date of approval of this amendment, the only SAEs to be reported to the sponsor are death during the hospital admission in which the participant was recruited (up to 30 days after admission; and not reportable if recruited in HDU/ICU setting), or congenital anomaly or birth defect occurring at any time. Other SAE categories shall not be reported to the sponsor unless they are related to the study. The publishing of safety outcome data for this trial is unchanged by this update.

13. Ethics, Oversight and Approvals

Declaration of Helsinki

The Investigators will ensure that this study is conducted according to the principles of the current revision of the Declaration of Helsinki.

ICH Guidelines for Good Clinical Practice

The Investigators will ensure that this study is conducted in full conformity with the ICH Good Clinical Practice (GCP) and local regulatory requirements.

Submissions to HRA, REC and local R&D

The protocol, informed consent forms, participant information sheet (and any other document requested) will be submitted to the Health Research Authority (HRA) for their processes including Regional Ethics Committee (REC) for written approval, and the study will not commence until all necessary HRA and REC approvals are in place. The Chief Investigator will submit and, where necessary, obtain approval from the REC for all subsequent substantial amendments to the protocol and informed consent document. Local R&D approval will be confirmed prior to study start.

Participant Confidentiality

All data will be anonymised: volunteer participant data will be identified by a unique study number in the CRF and database. A separate confidential file containing identifiable information will be stored in a secured location in accordance with the Data Protection Act 1998. Only the Sponsor's representative and investigators will have access to the information.

Investigator Responsibility

The Chief Investigator is responsible for the overall conduct of the study and compliance with the protocol and any protocol amendments. Responsibilities may be delegated to an appropriate member

of study site staff. Delegated tasks must be documented on a Delegation Log and signed by all those named on the list.

Monitoring

UHS as sponsor will put in place study monitoring based on study risk assessment at study set-up stage. Study monitoring will be conducted by UHS R&D Clinical Trials Project Managers as per the monitoring plan.

Publication Policy

The Investigators will be involved in reviewing drafts of the manuscripts, abstracts, press releases and any other publications arising from the study. Authorship will be determined in accordance with the ICMJE guidelines and other contributors will be acknowledged.

The study results are intended to be disseminated via peer-reviewed journals (which typically have summaries available on the internet), medical conference posters and presentations, and where appropriate, via select media outlets. Participants will therefore be able to access the study results via a range of methods. The Chief Investigator is responsible for the study data.

14. Finances and Indemnity

This is an NHS-sponsored study. If there is negligent harm during the clinical trial when the NHS body owes a duty of care to the person harmed, NHS indemnity covers NHS staff, medical academic staff with honorary contracts, and those conducting the trial. NHS Indemnity does not offer no-fault compensation and is unable to agree in advance to pay compensation for non-negligent harm.

15. Role of QIAGEN

The manufacturer of the QIAstat-Dx platform, QIAGEN (Hilden, Germany) will support this study by providing equipment and consumable free of charge. They have had no role in the conception or design of this study and will not have any role in the conduct of the study, data analysis and interpretation, or preparation of manuscript for submission to scientific journals. Only the research team and medical statistician will have access to the data prior to publication.

16. Laboratory analysis plan

Exploratory assays will be carried out on the samples collected in this study at the discretion of the Chief Investigator, with the purpose of studying localised and systemic infection and the human immune responses to infection. The samples acquired from participants and subsequent laboratory analysis will continue after participant recruitment has closed for a period of up to five years. After this period, further application to the relevant ethics committee may be required to continue storing and using the samples, or the Chief Investigator may deposit the samples in an appropriately licenced biobank, or destroy the samples.

The samples will be stored long-term in appropriate, storage conditions (e.g. -80°C freezers) within the Chief Investigator's institution. Access to these samples is restricted to the Chief Investigator's team and relevant laboratory managers.

The samples collected in this study may be used to evaluate the diagnostic accuracy of other infectionrelated diagnostic tests including those testing for COVID-19.

The gold standard assay for respiratory virus quantification is quantitative polymerase chain reaction (qPCR). qPCR will be used to detect and quantify pathogen presence and quantity in the various samples collected and measure changes in load over time (kinetics).

Samples may be used for host response gene expression studies, where messenger RNA (mRNA) from cells is measured to obtain a "snapshot" of which genes are being expressed. qPCR and whole genome high-density arrays may be used to compare gene expression examining for markers of infection. Techniques such as ELISA and ICS may be used to confirm the results. No studies concerning diseases or traits not connected with respiratory disease will be performed on these samples.

Other exploratory assays potentially include next generation sequencing of samples for detection of possible pathogens that are not conventionally tested for or are novel. In these studies, human genomic material will not be analysed and will be removed computationally by reference-guided mapping.

Samples may be also be tested for antibodies to coronaviruses (serology) and other respiratory viruses, and other immune responses including but not limited to cytokines, C reactive protein, and procalcitonin.

All samples are anonymised of personal identifiable information, and identified by the participant's study number. Anonymised clinical parameters collected can be correlated with these results. The consent provided by participants expressly permits further research on these samples. This work will primarily occur within the Clinical and Experimental Sciences (CES), Faculty of Medicine, University of Southampton, but collaboration with other institutions is at the discretion of the PI.

17. Other personnel and sponsor

Key study personnel in addition to the Chief Investigator & Co-investigators include:

• Clinical Research Fellows and other doctors in Infectious Diseases, Emergency medicine, and Acute Medicine, UHS.

• Research Nurses and Research Assistants at UHS.

The sponsor is University Hospital Southampton NHS Foundation Trust.

For the sponsor and R&D contact: [name], Clinical Trials Project Manager – UHS Sponsored Studies. [name]; [contact] or [contact].

18. References

¹WHO Coronavirus disease 2019 (COVID-19) Situation Report - 44 (4th March 2020); https://www.who.int/docs/default-source/coronaviruse/situation-reports/20200304-sitrep-44-covid-19.pdf?sfvrsn=783b4c9d_6 (Accessed 05 March 2020)

² Wu JT, Leung K, Leung GM. Nowcasting and forecasting the potential domestic and international spread of the 2019-nCoV outbreak originating in Wuhan, China: a modelling study [published online ahead of print, 2020 Jan 31]. *Lancet*. 2020; S0140-6736(20)30260-9.

³ Chen N, Zhou M, Dong X, et al. Epidemiological and clinical characteristics of 99 cases of 2019 novel coronavirus pneumonia in Wuhan, China: a descriptive study. *Lancet* 2020. 395(10223):507–513.

⁴ Pan X, Chen D, Xia Y, et al. Asymptomatic cases in a family cluster with SARS-CoV-2 infection. *Lancet* Infect Dis. 2020. S1473-3099(20)30114-6

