	Protocol non-compliance and deviations	.34

	Serious breaches of GCP or protocol
	Update to SAE reporting with Protocol Version 1.2
13.	Ethics, Oversight and Approvals3
D	eclaration of Helsinki3
IC	CH Guidelines for Good Clinical Practice3
S	ubmissions to HRA, REC and local R&D3
Ρ	articipant Confidentiality3
Ir	vestigator Responsibility3
N	1onitoring3
Р	ublication Policy3
14.	Finances and Indemnity3
15.	Role of QIAGEN3
16.	Laboratory analysis plan3
17.	Other personnel and sponsor3
18.	References3

1. Synopsis

Trial site

Southampton General Hospital, University Hospital Southampton NHS Foundation Trust, [name], UK.

Trial locations

Emergency department (ED), Acute Medical Unit (AMU), Respiratory High Dependency Unit (RHDU), General Intensive Care Unit (GICU), medical wards and other locations, within University Hospital Southampton NHS Foundation Trust (UHS).

Aim

To evaluate the clinical impact and real-world diagnostic accuracy of routine molecular point-of-care testing for respiratory viruses including SARS-CoV-2 (the cause of COVID-19) in adults presenting to hospital with suspected COVID-19 and/or acute respiratory illness (ARI).

Design

Non-randomised, interventional, controlled study.

Population

Adults aged 18 years old and over presenting to hospital with suspected COVID-19 and/or ARI.

Sample Size

1000 participants (500 participants in the intervention group and 500 in the control group).

Intervention

Combined nose and throat swab (and lower respiratory tract samples where available) tested by QIAGEN QIAstat-Dx Respiratory SARS-CoV-2 Panel at the point-of-care with results communicated to clinical and infection control teams in real time.

Control

Routine clinical care with testing for SARS-CoV-2 by laboratory RT-PCR performed in regional Public Health England (PHE) laboratory contemporaneously, in patients not included in the intervention.

Key Assessment

Evaluation of clinical outcome measures, implementation feasibility, and real-world diagnostic accuracy.

Timing

12 months: March 2020 to April 2021 (with up to 6 months for patient recruitment)

Plus a further five years after patient recruitment has ended for data and laboratory analysis of specimens

2. Overview

Background

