We will undertake a prospective, interventional, non-randomised, implementation study of mPOCT for COVID-19 in adults presenting to University Hospital Southampton NHS Foundation Trust. A brief validation and training phase will be followed by the post-implementation phase where patients will be recruited and tested at the point-of-care using the QIAstat-Dx Respiratory SARS-CoV-2 Panel. We will initially test patients suspected of COVID-19 based on current PHE case definitions and then progress to testing all patients with ARI as the outbreak becomes more widespread in the UK and the risks of admitting patients to hospital with unsuspected COVID-19 are high. Clinical and infection

control teams will be informed of these results in real time. The control group will consist of patients who were tested for SARS-CoV-2 by laboratory PCR but not recruited to the study during the same time period. This allows us to have a comparable control group as the outbreak progresses and hospital pathways change, as opposed to a pre-implementation group which predominantly is expected to consist of community-based patients tested in hospital for containment reasons. Only anonymised, routinely collected hospital data will be obtained for the control group. Outcome measures will be by assessed by retrospective case note analysis and will include: time to result, time in isolation facilities, detection of COVID-19 cases not initially suspected (based on current PHE case definition), antibiotic use, antiviral use, length of hospital stay, ward closures and hospital resource use. Multivariate analysis will be used to control for the effect of confounding variables between the groups.

Potential benefits to patients and the NHS

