We hypothesise that the use of a routine mPOCT for respiratory viruses including SARS-CoV-2 in adults presenting to hospital with suspected COVID-19 and/or ARI will dramatically reduce the time from patient presentation to results, compared to the current standard of PHE laboratory RT-PCR. We expect that timely detection or exclusion of COVID-19 will lead to improvements in early directed isolation facility and enhanced PPE use or de-isolation/de-escalation, in addition to other potential benefits such as reduced length of stay, improved use of antibiotics and antivirals and resource use and cost for the NHS. The detection of COVID-19 positive cases presenting to hospital and not initially suspected based on current the PHE case definition will prevent widespread nosocomial transmission of SARS-CoV-2 and associated hospital ward closures.

3. Abbreviations and Definitions

AE: Adverse Event AMU: Acute medical unit ARI: Acute respiratory illness CES: School of Clinical and Experimental Sciences, Faculty of Medicine University of Southampton **CI:** Chief Investigator COVID-19: Coronavirus disease 2019 CRF: Case Report Form ED: Emergency Department GICU: General Intensive Care Unit HRA: Health Research Agency ICU: Intensive care unit mPOCT: Molecular Point-of-Care test PCR: Polymerase Chain Reaction PHE: Public Health England PI: Principal Investigator POCT: Point-of-Care Test **PPE: Personal Protective Equipment REC: Regional Ethics Committee** RHDU: Respiratory High Dependency Unit RT-PCR: Reverse Transcriptase Polymerase Chain Reaction SAE: Serious Adverse Event

SARS-CoV-2: Severe acute respiratory syndrome coronavirus 2

UHS: University Hospital Southampton NHS Foundation Trust

WHO: World Health Organisation

4. Introduction

COVID-19

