Non-hospitalised hospital staff members may be included in the intervention phase of the study, if they satisfy the other inclusion & exclusion criteria. The same consent and study procedure processes are followed. However, their results will not be included in analyses of most outcome measures, with the exception of time to result. Days away from work may be used as an additional outcome measure.

Participant Withdrawal

A participant, or their consultee where a participant lacks capacity, may decide to withdraw from the study at any time, without giving reason, and with no detriment to their medical care or legal rights.

The chief investigator may withdraw a patient from the study in the interests of participant safety or the integrity of the research study, or on the advice of the sponsor's representative (R&D department).

Any patient, or their consultee where a patient lacks capacity, who is withdrawing from the study has the options withdraw and have data and/or samples collected so far retained, or withdraw and have their data and/or samples destroyed (but signed consultee declaration forms, minimal personal identifiable information to record the withdrawal, and any completed point-of-care test result will be retained). Although the study procedures are very brief, if a patient loses capacity after enrolment but before the study procedures are completed, consultee consent must be sought to continue with any study procedures, or the participant must be withdrawn.

A note to file would normally be sufficient to record any withdrawal.

7. Outcomes

Primary outcome

• The primary outcome measure is the time from COVID-19 test being requested to the result being available to clinical teams.

Secondary Outcomes

- The time from presentation to hospital to COVID-19 test result
- Time spent in COVID-19 assessment cohort area
- Time to definitive ward move
- Number of bed moves •
- Duration of hospitalisation •
- Number and proportion of clinically unsuspected COVID-19 positive patients detected •
- Proportion of patients treated with antibiotics
- Proportion of patients treated with single doses or brief courses (<48 hours) of antibiotics •
- Duration of antibiotic use, days
- Proportion of all influenza antiviral use occurring in influenza positive patients •
- Proportion of all influenza antiviral use occurring in influenza negative patients •
- Time from admission to influenza antiviral commencement

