Accepting that the prevalence of COVID-19 during the study is highly speculative at present, and so formal samples size calculation for diagnostic accuracy studies are not possible, testing 500 patients will allow us to make an ongoing assessment of the real-world diagnostic accuracy of the QIAstat-Dx Respiratory SARS-CoV-2assay compared to the current reference standard of laboratory PCR testing using the PHE RdRP assay.

The control group will be 500 patients for an adequate comparison.

9. Data collection

Demographic and clinical data will be collected for all patients at enrolment including: age, sex, ethnicity, smoking status, vaccination status, co-morbidities, medication use, symptoms, duration of illness prior to hospitalisation, observations (pulse rate, respiratory rate, blood pressure, oxygenation status), laboratory results, radiology results, antimicrobial and antiviral use prior to hospitalisation and provisional diagnosis. Data will be recorded on a Case Report Form, which we intend to be electronic (ALEA). Once patients have been discharged or after 30 days (whichever is soonest), clinical data will be collected retrospectively from electronic and physical case notes including: use of antivirals, duration of antivirals, time from assessment to antiviral use, use of side room facilities, time from assessment to isolation facility use, time to clinical stability, duration of supplementary oxygen use, duration of hospitalisation, complications including ICU and RHDU admission, representation and readmission to hospital within 30 days, final diagnosis and mortality. The number of diagnostic tests and procedures performed will also be recorded and data will also be collected on the turnaround time of respiratory virus test results in each group.

10. Data Management

The subjects' anonymity will be maintained. The study team will keep a log of each subject's name, hospital ID number, date of birth, and unique participant trial number. The participant details will be recorded on the secure NHS Edge system in a similar manner, including NHS number. This participant trial number is used on documents after screening to maintain confidentiality. Documents that are not anonymous (e.g. signed informed consent forms) will be maintained separately, in strict confidence.

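### Time to result is compared only with other, non-recruited patients, so the hours saved may carry residual confounding; a supportive within-patient comparison would check this where timed laboratory PCR exists

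*Protocol*

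**What the plan says.** - **Outcome.** Protocol Section 7: "The primary outcome measure is the time from COVID-19 test being requested to the result being available to clinical teams".
- **Hypothesis.** Section 2 (Potential benefits) expects that point-of-care testing "will dramatically reduce the time from patient presentation to results, compared to the current standard of PHE laboratory RT-PCR". The clock here starts at presentation, not at request.
- **Comparator.** Section 2 (Methods) defines controls as "patients who were tested for SARS-CoV-2 by laboratory PCR but not recruited to the study during the same time period". The Synopsis likewise describes laboratory testing done "contemporaneously, in patients not included in the intervention". Section 2 argues that a same-period group stays comparable as the outbreak and hospital pathways change.
- **Analysis.** Section 11: "The primary outcome measure (median duration of isolation facility use) will be compared between the groups using the Mann-Whitney U test". It adds: "Multivariate analysis will be performed to adjust for confounding variable in view of the non-randomised nature of the study". No within-patient comparison of the two turnaround times is described.
- **Laboratory PCR in participants.** Objective 3 (Section 5) and the accuracy outcomes (Section 7) compare the point-of-care assay with PHE laboratory PCR. Section 8 says that "testing 500 patients will allow us to make an ongoing assessment of the real-world diagnostic accuracy".
- **Timing data.** Section 9: "data will also be collected on the turnaround time of respiratory virus test results in each group".

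**The concern.** The groups are formed by whether a patient was recruited. Under Section 6, a participant must consent or have consultee agreement, be recruitable within 24 hours of presentation, and be swabbed by trained research staff. All patients with acute respiratory illness are to be approached, so controls are largely those who were missed, could not be recruited in time or declined. Being missed may depend on hour, weekday or ward, and the same factors may affect how fast a laboratory result comes back.

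Eligibility also differs. Controls must have acute respiratory illness, while the intervention group may include patients without it. Non-hospitalised staff count towards time to result in the intervention phase, and no matching rule is given for controls.

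The headline result is the number of hours saved. If laboratory turnaround in controls is not what participants would have had, that number is off, however large the sample. The same-period design deals with calendar drift but not with this selection. No stated analysis checks whether the control group is comparable on laboratory turnaround.

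**Working it through.** **1. What can be reproduced.** The only sample-size arithmetic is 500 + 500 = 1000, which agrees. No alpha, power, effect size or SD is given, because the number was set by kit supply.

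**2. Precision is not the issue.** Assume two-sided alpha 0.05 and equal SDs. Detectable difference = (z for alpha + z for power) × √(2/500), that is:
- 80% power: (1.960 + 0.842) × 0.0632 = 0.177 SD
- 90% power: (1.960 + 1.282) × 0.0632 = 0.205 SD

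With a Mann-Whitney efficiency of 0.955 these become 0.181 and 0.210 SD.

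**3. Size of the contrast from the protocol's own figures.** Section 4 gives point-of-care results in about 1 hour, and under 2 hours in the earlier trials. It gives laboratory results in 1–2 days in the earlier trials and 3–4 days on the pathway current at the time of writing.
- Laboratory 24–48 h: 24 − 2 = 22 h up to 48 − 1 = 47 h
- Laboratory 72–96 h: 72 − 2 = 70 h up to 96 − 1 = 95 h

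**4. What an assumed residual bias would do.** Bias as a share of the contrast:

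| Assumed bias | Laboratory 24 h (contrast 22–23 h) | Laboratory 96 h (contrast 94–95 h) |
|---|---|---|
| 2 h | 9% | 2% |
| 6 h | 26–27% | 6% |
| 12 h | 52–55% | 13% |

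Even 12 h is below the smallest contrast of 22 h, so the sign would hold.

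**5. How such a bias could arise (illustration only).** Assume laboratory turnaround is a mixture of a fast and a slow stratum, each lognormal with log-scale SD 0.6. The median m solves p·Φ[(ln m − ln slow)/0.6] + (1 − p)·Φ[(ln m − ln fast)/0.6] = 0.5, where p is the slow share. Participants' own laboratory tests have p = 40%.

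| Stratum medians | Slow share in controls | Control median | Participants' laboratory median | Difference |
|---|---|---|---|---|
| 36 / 84 h | 50% | 55.0 h | 49.8 h | 5.2 h (+10%) |
| 36 / 84 h | 60% | 60.7 h | 49.8 h | 10.9 h (+22%) |
| 24 / 48 h | 50% | 33.9 h | 31.4 h | 2.5 h (+8%) |
| 24 / 48 h | 60% | 36.7 h | 31.4 h | 5.2 h (+17%) |

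36 and 84 h are the midpoints of 1–2 and 3–4 days. The strata, shares and SD are assumptions, no adjustment is modelled, and the sign reverses if the imbalance does.

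**6. Would adjustment cover it?** Section 6 (Control group) lists age, sex, co-morbidity, observations, blood results, length of stay and time to result. Section 9 lists demographic and clinical items for enrolled patients. Neither names hour, weekday or ward. Both lists are open-ended, so these could be added, but nothing stated ensures it.

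**7. Does a same-patient comparator exist?** Sensitivity, specificity and agreement need a laboratory PCR result in point-of-care participants, so some pairs are presupposed. Section 6 (Procedures), however, describes no parallel routine PCR with timestamps. The only further upper-airway swab offered to all participants is optional. Section 16 allows stored samples to be tested later. The number of usable pairs is therefore unknown.

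**8. What pairing does for precision.** The standard error in SD units is √(2(1 − ρ)/n), with ρ the correlation between the two times, against √(2/500) = 0.0632 unpaired.
- n = 500: 0.0632 (ρ = 0), 0.0447 (ρ = 0.5)
- n = 250: 0.0894 (ρ = 0), 0.0632 (ρ = 0.5)

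The gain from pairing is control of confounding, not necessarily precision.

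**The case against.** The strongest reply is that the same-patient comparator is inferred. Objective 3 needs a laboratory result, not a real-time one. A reference PCR run on the optional swab or on stored material has no clinical turnaround, and collecting turnaround in each group may mean one kind of test per group. This stands. A reader might infer that a timed laboratory PCR exists for every participant and is being left unused; the protocol does not say so.

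Second, a reader might infer that the hypothesis names a test as comparator and that the control group does not match it. The hypothesis can equally be read as comparing care pathways, and the Synopsis defines control as routine care with laboratory testing. On that reading there is no mismatch.

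Third, confounding is acknowledged: same-period controls are justified and multivariate adjustment is planned. This stands too, but the listed items do not name the factors most likely to link recruitment with laboratory speed.

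Fourth, a paired analysis has weaknesses of its own. It covers only recruited patients with both tests. Laboratory requests may be dropped or handled less urgently once the point-of-care result is known, and the two request clocks may start at different times. It can only be supportive.

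Fifth, a supportive analysis could sit in a separate SAP that was not available. Nothing in the protocol excludes it. But the comparator and the between-group analysis are fixed here, in a section that is itself titled as the statistical analysis plan.

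**Conclusion.** The concern holds as a risk of residual confounding in the size of the primary effect. Time to result is compared only between different patients, selection may follow factors not named for adjustment, and no stated check tests comparability on laboratory turnaround. The direction of effect is unlikely to change.

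A reader might take the illustrated 2.5 to 10.9 hours as the bias in this trial. The documents do not support that. The figure depends on assumed strata, shares and spread, without adjustment, and it mixes turnaround for other respiratory viruses in earlier trials with an early SARS-CoV-2 pathway. It shows what a moderate imbalance could do, not what will happen.

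Before any primary estimate can be defined, the protocol must settle which outcome is primary. Section 7 names time to result, while Section 11 attaches the Mann-Whitney test to duration of isolation facility use. The start of the clock (request in Section 7, presentation in the Section 2 hypothesis) should be settled with it. The point merits a change because the remedy is inexpensive and bears directly on the headline number.

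**What to change.** In Protocol Section 11:

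1. Reconcile the primary outcome named there with Section 7, and state the start of the clock.
2. Keep the between-group comparison with multivariate adjustment. The control group is still needed for the clinical outcomes.
3. State whether participants have a routine laboratory SARS-CoV-2 PCR with recorded request and result times.
4. Where they do, add a pre-specified supportive paired analysis in participants whose routine laboratory PCR was requested in the same presentation, excluding stored or batch-tested samples. Use the Wilcoxon signed-rank test and report the median within-patient difference in request-to-result time with a 95% CI.
5. Compare laboratory turnaround in these participants with that in controls, as a check on the Section 2 claim of a comparable control group.
6. Report the number of pairs and the order of the two requests.

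**Cost.** A few sentences of analysis text. If routine laboratory timestamps are already captured for participants, no further data are needed; if not, they must be retrieved from the laboratory system. Pairs will exist only where a routine PCR was done, and laboratory handling may have been affected by knowledge of the point-of-care result, so the paired estimate should be labelled supportive.
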